## **Analyses of Other Endpoints and Subgroups**

Descriptive summaries will be reported for the composite safety outcome of grade 3 or 4 AE, SAE, or death for the one versus two dose strategy. Similar summaries will be reported for the one vs two dose strategies as well as for the immediate vs deferred strategies for the composite endpoint of SAE or death through Week 24. Non-adherence to the assigned vaccination schedule will be summarized similarly as well.

A number of additional subgroup analyses are planned for each treatment comparison, taking advantage of the data collected at baseline and during follow-up on TICO. Subgroup analyses for each primary objective and the comparisons of TICO active and placebo groups will be performed using regression analysis. In addition to subgroups according to the other factor in the factorial design and the randomization assignment in TICO, prior vaccination at entry to TICO, subgroups according to age, gender, race/ethnicity, geographic region, duration of infection at time of randomization, severity of infection as measured by the highest ordinal category experienced and time to sustained recovery, baseline antigen and antibody level in TICO, and baseline antibody level at the time of randomization to VATICO will be carried out. These analyses will be performed by including an interaction term with treatment in the regression model with the antibody level prior to randomization into VATICO included as a covariate.

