## Analysis of the Primary Efficacy Endpoint

Analysis will be intention to treat and include all participants including those assigned an investigational agent in TICO and those assigned a placebo in TICO. Quanterix antibody levels at VATICO baseline and at Weeks 12, 24, and 48 will be summarized with box plots by immediate/ deferred, by one/two doses, and by each arm in the 2x2 factorial.

For the comparison of Quanterix antibody levels at Week 48 (the primary endpoint), levels will be log10 transformed and evaluated with analysis of covariance that includes indicators for each factor of the factorial. An interaction test will be carried out between the two factors as well. The antibody level prior to randomization into VATICO, vaccination prior to enrolling in TICO, and assignment to an investigational agent in TICO will be included as covariates to reduce the residual standard error and improve efficiency of the primary comparisons.

Table 1. Power to detect various geometric mean ratios with n = 66 VATICO participants assuming residual standard error of 0.6787 estimated from AZ and MP TICO participants Quanterix antibody levels at baseline and 28 weeks.

	Geometric Mean Ratio					
	1.2	1.5	2.0	3.0	4.0	6.0
Power	7%	18%	43%	80%	94%	>99%

The log10 transformation will be undertaken as is conventional for NAb measurements (as the distribution of log responses is generally closer to a normal distribution), and then the estimates and confidence intervals will be anti-logged to provide estimates and confidence intervals for the ratio of GMRs. A GMR of one indicates that there is no difference between treatment groups in NAb response, for example, among participants who were randomized to immediate compared with those randomized to deferred vaccination. A GMR less than 1.0 provides indication of lower NAb response among those who received immediate compared to those who received vaccination deferred.

The percentage of participants with a 4-fold increase in antibody levels from baseline will be summarized for each factor in the 2x2 factorial using Mantel-Haenszel chi-square statistics.

These analyses will be repeated for participants randomized to an investigational agent in TICO and to a placebo in TICO. These analyses will also be repeated for the Quanterix antibody levels at Week 12 as well as at Week 24.

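### Does the SAP's subgroup model adjust a TICO active-versus-placebo comparison for variables measured after TICO randomization?

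*SAP*

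**What the plan says.** In the SAP, Analyses of Other Endpoints and Subgroups, "subgroup analyses are planned for each treatment comparison, taking advantage of the data collected at baseline and during follow-up on TICO". The next sentence reads "Subgroup analyses for each primary objective and the comparisons of TICO active and placebo groups will be performed using regression analysis". Each subgroup analysis is an interaction between treatment and the subgroup variable, "in the regression model with the antibody level prior to randomization into VATICO included as a covariate".

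The subgroup variables fall into three kinds:

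- **Fixed before TICO randomization:** age, gender, race/ethnicity, region, vaccination before TICO entry, and "baseline antigen and antibody level in TICO".
- **Arising after TICO randomization but before VATICO randomization:** "severity of infection as measured by the highest ordinal category experienced and time to sustained recovery" and "baseline antibody level at the time of randomization to VATICO".
- **Randomized assignments:** "the other factor in the factorial design and the randomization assignment in TICO".

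Duration of infection is also listed, without saying at which of the two randomizations.

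The section Analysis of the Primary Efficacy Endpoint uses TICO assignment as a covariate for efficiency and repeats the vaccination comparisons within the agent and placebo groups. Its example of a geometric mean ratio is immediate versus deferred vaccination. The section Analysis of Baseline Characteristics makes clear that TICO follow-up precedes the VATICO randomization.

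**The concern.** The sentence joins two kinds of comparison with a plain conjunction and gives both the same model. For immediate versus deferred vaccination, or one versus two doses, every listed variable is a legitimate baseline variable. For agent versus placebo in TICO, three of them are not: VATICO-baseline antibody, highest ordinal category and time to sustained recovery could each have been changed by the agent.

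Adjusting for antibody at VATICO entry would remove the part of the agent's effect that passes through it. With an unmeasured common cause of the two antibody levels, it could even reverse the sign. Splitting on a severity measure that the agent changed could give a TICO ratio different from 1 within both halves, although the agent had no effect on antibody. A reader who took such estimates as total effects of the TICO agent would be misled. On the face of it, the TICO comparison needs its own covariate set and subgroup list.

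**Working it through.** **1. Inputs.** The SAP gives n = 66 and a "residual standard error of 0.6787 estimated from AZ and MP TICO participants Quanterix antibody levels at baseline and 28 weeks" (log10 scale). Assumed, because the documents give no values: two-sided 5% tests; equal groups; the agent's fold effect T on VATICO-baseline antibody; the slope b of later antibody on that level (0.3 to 0.7); the shift a in severity caused by the agent, in SD units (0.2 to 0.5); and the residual correlation r of severity with later antibody (0.3 to 0.5).

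**2. The plan's own figure.** With 33 per group, the noncentrality is log10(GMR) / (0.6787 × sqrt(2/33)). At GMR 3 this is 0.477/0.167 = 2.86. With 64 degrees of freedom, the power for GMR 1.2, 1.5, 2, 3, 4 and 6 is 7.5%, 18.0%, 42.7%, 80.3%, 94.4% and 99.6%. Table 1 prints 7%, 18%, 43%, 80%, 94% and >99%. It reproduces to within one point and does not depend on the question here.

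**3. Which comparison is meant?** TICO assignment is itself a listed subgroup, and it cannot be a subgroup of its own contrast. The other factor of the factorial is meaningful as a subgroup only if treatment is a vaccination factor. The primary-endpoint section repeats the vaccination analyses within TICO groups, and no section supplied sets out a main agent-versus-placebo analysis. All of this fits vaccination effects compared across TICO groups.

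**4. If a TICO contrast is fitted: precision.**

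- SE of a TICO log10 ratio in a subgroup of 33: 2 × 0.6787/sqrt(33) = 0.236.
- SE of the interaction between two such subgroups: 0.236 × sqrt(2) = 0.334.
- 95% confidence factor: 10^(1.96 × 0.334) = 4.5 either way.

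**5. Effect of the antibody covariate on the interaction.** Shift = b × log10(T1/T2), where T1 and T2 are the agent's effects on VATICO-baseline antibody in the two subgroups. Results for b = 0.3, 0.5 and 0.7:

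| T1 versus T2 | Shift in SE | Rejection rate of a nominal 5% test |
|---|---|---|
| equal | 0, 0, 0 | 5% |
| 1.25 versus 1 | 0.09, 0.15, 0.20 | 5.1%, 5.2%, 5.5% |
| 1.5 versus 1 | 0.16, 0.26, 0.37 | 5.3%, 5.8%, 6.6% |
| 2 versus 1 | 0.27, 0.45, 0.63 | 5.8%, 7.4%, 9.7% |

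When the subgroups are vaccination arms, the expected shift is zero. Those arms are randomized after the covariate is measured, so T is the same in both on average.

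**6. Effect of the antibody covariate on a subgroup-specific TICO ratio.** The total ratio is divided by T^b. At T = 2 that is 2^0.3 = 1.23 to 2^0.7 = 1.62; at T = 1 it is 1.

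**7. Split on post-TICO severity, with no agent effect on antibody.** Let severity be S = U − aA, where A marks the agent and U is standard normal, and let later antibody be 0.6787 × (rU + noise). For a split at the pooled median, the log10 TICO difference in each half is

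r × 0.6787 × [φ(a/2)/(1 − Φ(a/2)) − φ(a/2)/Φ(a/2)].

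- a = 0.2: ratio 1.06 (r = 0.3) to 1.10 (r = 0.5).
- a = 0.5: ratio 1.16 to 1.28, at most 0.46 SE in a half of 33.

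The expression is the same in both halves, so the interaction shift is exactly zero. With a 25/75 split the interaction SE is 2 × 0.6787 × sqrt(1/16.5 + 1/49.5) = 0.386. The shift is 0.012 to 0.051 log10, or 0.03 to 0.13 SE.

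**8. Price of dropping the covariate.** If VATICO-baseline antibody correlates 0.3 to 0.7 with the outcome (assumed), residual SD rises by 1/sqrt(1 − r²), that is 5% to 40%. If TICO-baseline antibody recovers half of the explained variance, the factor is sqrt((1 − r²/2)/(1 − r²)), a rise of 2% to 22%.

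**The case for a change.** The best argument for a change is that the sentence sets the TICO comparisons beside the primary objectives as a separate item, and then lists TICO assignment again as a subgroup. The second mention is redundant if the first meant only subgrouping by TICO arm. An analyst could therefore fit a TICO contrast with the stated model, and the timing fault would be real: the shifts are systematic even where they are smaller than sampling error. A short restriction to pre-TICO variables would cost little text.

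The timing point stands, and so does the ambiguity. The need for a restriction does not. The SAP never says that a total effect of the TICO agent is sought, and an adjusted contrast could be a direct-effect question. Dropping the covariate would not recover a randomized comparison either. Under the Letter of Amendment's consent correction, people vaccinated after joining TICO cannot enter VATICO, so entry already depends on events after TICO randomization. A rule admitting only variables measured before TICO randomization would, read literally, also bar the vaccination factors, which are randomized and harmless as subgroups. It would give up precision in an analysis whose interval already spans a factor of 4.5 either way.

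**Conclusion.** The concern does not call for a change. It rests on one reading of an ambiguous phrase, and the surrounding text fits the other reading at least as well. There the randomized factor is the VATICO one and the adjustment is correct.

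If a TICO contrast were fitted, subgroup-specific ratios would not be total effects: they would be divided by 1.23 to 1.62 if the agent doubled VATICO-baseline antibody. The planned interaction term would shift by nothing, or by up to 0.13 SE for the severity splits examined. For the covariate it would shift by up to 0.63 SE, and only under an assumed twofold difference between subgroups in the agent's effect on baseline antibody. These sizes depend on assumed T, b, a and r and on equal allocation; the documents supply only n = 66 and 0.6787.

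This is a gap that analysts fill sensibly by saying which comparison they ran and that any TICO contrast is among TICO participants who joined VATICO. One SAP passage and the full protocol were not available, so the objective may be defined there. The primary comparisons and Table 1 stand either way.

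### Does naming only one covariate for the subgroup interaction models, against three in the primary ANCOVA, leave the analysis in conflict?

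*SAP*

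**What the plan says.** In the SAP, Analysis of the Primary Efficacy Endpoint, log10 antibody levels at Week 48 are compared by "analysis of covariance that includes indicators for each factor of the factorial". The next sentence adds: "An interaction test will be carried out between the two factors as well". Three covariates are then listed (antibody level before VATICO randomization, vaccination before TICO, assignment to an agent in TICO), which "will be included as covariates to reduce the residual standard error and improve efficiency of the primary comparisons".

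In the SAP, Analyses of Other Endpoints and Subgroups, the list of subgroups opens with a reference to "subgroups according to the other factor in the factorial design and the randomization assignment in TICO", then gives prior vaccination, age, gender, race/ethnicity, region and several measures of disease and antibody status. The method is "including an interaction term with treatment in the regression model with the antibody level prior to randomization into VATICO included as a covariate". The scope sentence reads: "Subgroup analyses for each primary objective and the comparisons of TICO active and placebo groups will be performed using regression analysis".

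The material supplied does not say whether the other factor's indicator, prior vaccination and TICO assignment stay in the subgroup models. The supplied protocol document is only a letter of amendment on visit contacts and consent wording. The main protocol is not included, and some SAP text was removed before review.

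**The concern.** Read literally, the two sections give different recipes for what may be the same test. The factor-by-factor interaction sits beside a three-covariate ANCOVA in one place. In the other it can be read as a subgroup analysis with one named covariate. If the subgroup model were simply the primary ANCOVA plus an interaction, there would be no need to name again one covariate already in it, so the shorter model is a natural reading.

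Three things would be at stake:

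- **Reproducibility.** Two analysts could report different p-values for one interaction, and an unfixed choice could be made after seeing the data.
- **Precision.** For subgroups such as age or region, leaving out the other factor's indicator would put that factor's effect into the residual.
- **Estimand.** The scope sentence also covers comparisons of TICO active and placebo groups. Antibody level before VATICO is measured after TICO assignment, so adjusting for it could remove part of a TICO effect.

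**Working it through.** **Inputs.** From the SAP: n = 66 and residual SD 0.6787 on the log10 scale (Table 1). Assumed, because the documents do not give them: two-sided alpha 0.05, equal allocation, 20% vaccinated before TICO, 50% on a TICO agent, and a share R² of residual variance explained by those two covariates together (split equally), ranged from 0 to 0.20.

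**1. Reproduce Table 1.** Main-effect SE = 2 × 0.6787/√66 = 0.167. At GMR 2, log10(2) = 0.301 and 0.301/0.167 = 1.80, giving 43% power by noncentral t. At GMR 3, 0.477/0.167 = 2.86, giving 80%. Both match the table.

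**2. Precision of the interaction.** SE = 4 × 0.6787/√66 = 0.334, twice the main-effect SE. Error degrees of freedom are 59 with three covariates and 61 with one. The 95% interval for a ratio of GMRs is the estimate multiplied and divided by about 4.66 in either case if SD is 0.6787. Power at a 3-fold ratio is 29%.

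**3. Effect of dropping the two covariates.** Residual SD rises by 1/√(1 − R²), while fitting two fewer terms gives back about 1.4% (simulated factor 0.986 at R² = 0, 10,000 trials per setting, 50:50 subgroup). The product matches the simulation at each R²:

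| R² | 1/√(1 − R²) | × 0.986 | Simulated SE ratio, short/full |
|---|---|---|---|
| 0 | 1.000 | 0.986 | 0.986 |
| 0.05 | 1.026 | 1.012 | 1.012 |
| 0.10 | 1.054 | 1.039 | 1.039 |
| 0.20 | 1.118 | 1.102 | 1.102 |

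A separate simulation of the factor-by-factor test itself gave about 0.98, 1.01, 1.04 and 1.10. At R² = 0.10 the short-model SD is 0.6787/√0.90 = 0.715, and power at a 3-fold ratio goes from 29.0% to 26.5%.

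**4. Effect of also dropping the other factor's indicator.** This cannot affect the factor-by-factor test, where the other factor is the subgroup and its main effect enters with the interaction. For subgroups such as age or gender, the added variance is (log10 GMR)²/4:

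- GMR 2: 0.0227 against 0.6787² = 0.4606, or 4.9%; SE × √1.049 = 1.024.
- GMR 3: 0.0569, or 12.4%; SE × √1.124 = 1.060.

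With all three terms out, the simulated net SE ratio is 1.000 (GMR 2) or 1.035 (GMR 3) at R² = 0, and 1.052 or 1.085 at R² = 0.10. If only a GMR-3 factor indicator is dropped, power at a 3-fold ratio goes from about 29% to 26%.

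**5. Bias.** The mean error in the interaction estimate was at most 0.002 log10 in every model, as expected when the contrast is randomized and only precision covariates are left out.

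**6. What 0.6787 represents.** Table 1 says it came from antibody levels at baseline and 28 weeks and mentions no other covariate, so it may already be the residual SD of the shorter model. The SE ratios in steps 3 and 4 treat it as the full-model value. Under the other reading the ratios in step 3 stand, but the absolute powers shift.

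**The case for a change.** The best argument for a change is that average precision is not the only issue. In 5,000 simulated trials per setting, with a true 3-fold ratio, the one- and three-covariate models fell on opposite sides of 0.05 in 5%, 7%, 9% and 12% of trials at R² = 0, 0.05, 0.10 and 0.20. With no interaction the figure was 1.5% to 4%. The two estimates differed by a median of 1.07- to 1.29-fold. One sentence would close the gap at little cost.

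Those figures stand, and stating the model would be tidy. They do not show that the plan is wrong:

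- The conflict is not firmly in the text. The subgroup sentence does not say that antibody level is the only covariate. The primary section ties its three covariates to the primary comparisons and does not expressly assign them to the interaction test. The subgroup list introduces the other factor and TICO assignment as items to which further subgroups are added. Both already appear in the primary section, as the interaction test and the repeat by TICO arm, so this may be a back-reference. That reading is plausible, not certain: prior vaccination follows them and has no such earlier subgroup analysis.
- Disagreement around 0.05 is what two valid models will show when power is near 29%. A 1.29-fold gap is small beside an interval that spans a factor of 4.66 each way.
- A short covariate list is a defensible choice at n = 66, where subgroups such as race/ethnicity and region may add several parameters of their own.

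The TICO point rests on an assumed estimand. The SAP does not define the comparison of TICO active and placebo groups. It may mean comparing vaccine effects between those groups, in line with the repeated analyses in the primary section. Antibody level before VATICO is then a proper pre-randomization covariate, and replacing it with the TICO value, available under "baseline antigen and antibody level in TICO", would discard useful information. The worry holds only if a total TICO effect is meant.

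**Conclusion.** No change to the plan is needed. The SAP leaves a detail of its secondary models open, and an analyst would ordinarily fill it by adding the subgroup main effect and its interaction to the primary ANCOVA, reporting the factor-by-factor test once. The shorter model would also give unbiased vaccine contrasts. For the factor-by-factor test the choice moves the SE by about -1.5% to +4% at R² from 0 to 0.10, and +10% at 0.20. For other subgroups, if the other factor's indicator is dropped too, the change is 0 to +3.5% at R² = 0 and about +5% to +8.5% at R² = 0.10, for a factor effect of GMR 2 to 3. These sizes rest on an R² that the documents do not give, on equal allocation, and on 0.6787 being the full-model SD. The gain from a change has no documented size, and for the factor-by-factor test no documented sign. The primary main-effect model and Table 1 are unaffected.
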